7.2.1.2.5 Serum protein electrophoresis (SPEP)

Serum protein electrophoresis (SPEP) will be performed by the local laboratory at screening and on the same schedule as radiological tumor assessments (see [Section 7.2.1.2.3](#)) only if abnormal M-protein is detected at screening.

7.2.1.2.6 Positron emission tomography (PET)

The use of Positron emission tomography (PET) is not standard in Novartis Oncology Lymphoma studies. PET evaluations that have been done as standard of care prior to enrollment will be recorded in the eCRF. Repeat PET will be required only for patients who have responses of CR for the purpose of this study and should be done within +/- 7 days of the CT or MRI to confirm CR. Refer to [Appendix B](#) for lesion measurements.

7.2.1.3 Symptomatic multiple myeloma

[Please note that these assessments are for ongoing patients and no new patients with symptomatic myeloma will be enrolled]

Response will be evaluated using the International Myeloma Working Group (IMWG) Uniform Response Criteria for Multiple Myeloma. For complete details, refer to [Appendix O](#).

Clinical evaluation and disease assessments will be performed periodically, as is indicated in [Table 7-1](#), based on a skeletal survey Urine protein electrophoresis (UPEP), Free light chain, Serum Protein electrophoresis (SPEP), bone marrow biopsy, and MRI/CT Scans (For plasmacytoma only).

7.2.1.3.1 Skeletal survey

Skeletal survey will be performed at screening and if clinically indicated as outlined in [Table 7-1](#).

7.2.1.3.2 Urine protein electrophoresis (UPEP)

Urine protein electrophoresis (UPEP) will be performed by the local laboratory at screening, every 8 weeks (± 4 days) after first dose of study drug (Day 1 of every odd cycle) and EOT.

7.2.1.3.3 Free Light Chain

Free Light Chain will be performed by the local laboratory at screening and on the same schedule as UPEP assessments (see [Section 7.2.1.3.2](#)).

7.2.1.3.4 Serum protein electrophoresis (SPEP)

Serum protein electrophoresis (SPEP) will be performed by the local laboratory at screening and on the same schedule as UPEP assessments (see [Section 7.2.1.3.2](#)).

7.2.1.3.5 MRI/CT scans (for plasmacytoma only)

For patients with plasmacytoma, a MRI/CT scan will be performed by the local laboratory at screening and on the same schedule as UPEP assessments (see [Section 7.2.1.3.2](#)).

7.2.1.3.6 Bone marrow assessment

Information on the patient bone marrow involvement prior to study entry must be present in his/her source documents. Prior tumor bone marrow involvement should be entered on the corresponding eCRF.

Core bone marrow biopsy is required to confirm Complete Responses (at the first occurrence of radiological and clinical evidence of CR) in patients with bone marrow tumor involvement prior to study treatment who achieve Complete Response based on clinical and radiological evidence. The biopsy sample on which this determination is made must be adequate (with a goal of > 20 mm unilateral core). Bone marrow biopsy should be obtained no later than at the next visit immediately following clinical and radiological evidence of CR (i.e. < 28 days ± 7 days from the date of the radiological assessment, on which the CR is based on).

7.2.1.4 Leukemia

[Please note that these assessments are for ongoing patients and no new patient with Leukemia will be enrolled]

Response for AML will be evaluated using the revised recommendations of the International Working Group (IWG) as noted in [Cheson \(2003\)](#) ([Appendix E](#)). Response for ALL will be evaluated using guidelines adapted from NCCN Guidelines Version 1.2013 ([Appendix F](#)). CML will be evaluated using guidelines adapted from NCCN Guidelines Version 4. 2013 ([Appendix G](#)). The response for CLL will be evaluated using the revised recommendation of the IWG as noted in [Hallek \(2008\)](#) ([Appendix H](#)). The response for myelodysplasia (MDS) will be evaluated using the revised recommendation of the IWG as noted in [Cheson \(2006\)](#) ([Appendix L](#)). The response for polycythemia vera (PV) and essential thrombocythemia (ET) will be evaluated using the recommendation of IWG-MRT as noted in [Barosi \(2013\)](#) ([Appendix J](#) and [Appendix K](#) respectively). The response for myelofibrosis (MF) will be evaluated using IWG-MRT as noted in [Tefferi \(2013\)](#) ([Appendix I](#)).

Clinical evaluation and disease assessments for AML, ALL, CML, MDS, PV, ET, and MF will be performed periodically, as is indicated in [Table 7-1](#), based on peripheral blood and bone marrow assessment as well as the presence or absence of extramedullary disease, and organomegaly, and evaluation of transfusion dependency. For MF and PV, the Myeloproliferative Neoplasm (MPN) Symptom Assessment Form Total Symptom Score (MPN-SAF TSS) will be completed as is indicated in [Table 7-1](#).

Clinical evaluations and disease assessments for CLL will be performed periodically as is indicated in [Table 7-1](#), based on the lymphoma assessments schedule for evaluation of physical examination for superficial disease and B symptoms, radiological evaluation, core bone marrow biopsy (only to confirm complete responses in patients with bone marrow tumor involvement prior to study treatment) and Rai staging criteria ([Appendix D](#)). Peripheral blood, and the presence or absence of extramedullary disease and organomegaly will also be performed on the same schedule as other leukemia evaluations as indicated below.

To assess response, the time interval between bone marrow and blood assessments may not exceed 5 days. If the time interval is more than 5 days, response status cannot be assessed at that time point. Regular bone marrow assessments are not required after achieving a CR unless indicated by blood counts or clinical assessments or specified in the protocol

The response assessment date is defined as the last of all dates of measurements which are required to qualify for a response category within the period listed above. This rule applies also in case of multiple measurements of the same variable. In case of relapse, the first of all measurement dates associated with a disease assessment will be used as assessment date. The assessment date will be used for the derivation of the time-to-event endpoints.

7.2.1.4.1 Peripheral blood evaluation for CBC

Peripheral blood evaluations will be performed by the local laboratory at screening, Day 1 and Day 15 of Cycles 1 and 2, at Day 1 of each subsequent cycle, and at EOT.

Peripheral blood evaluation for CBC will be taken from the same sample and include evaluation of blast, neutrophil, and platelet cell count.

7.2.1.4.2 Bone marrow assessment

Bone marrow will be assessed for blast cell count at screening, to confirm response of CR or if clinically indicated.

Percent blast cell count will be determined by cytological examination. This assessment can be performed in terms of bone marrow aspirate and/or biopsy. Results from these tests are considered to be interchangeable to assess blasts counts. In case both aspirate and biopsy were done, both tests will be considered for response assessment:

In case of only one assessment with non-missing values: Data of the non-missing test result will be used.

In case of both assessments with differing, non-missing data: For blast counts, the highest value will be considered. For Auer rods, the positive finding will be considered, if applicable

7.2.1.4.3 Physical examination for extramedullary disease and/or organomegaly

[figure not shown]
Extramedullary involvement (CNS and/or soft tissue) is to be assessed at each visit for response assessment. Presence with specification of location or absence of extramedullary disease is to be captured in the eCRF. Extramedullary disease is to be assessed via clinical examination or relevant imaging techniques as clinically appropriate.

In case of extramedullary disease at baseline or (re-)appearance during the study, the lesions need to be confirmed cytologically if technically and/or clinically feasible. A clinical assessment will be made in case a cytological confirmation is not possible

The presence of organomegaly (hepatomegaly and/or splenomegaly) is to be assessed at baseline at visits as part of the response assessment. The modality used: scan or palpation is to be noted.

7.2.1.4.4 Assessments of chromosomal abnormalities

Information on the patient's chromosomal abnormalities/karyotyping based on documented history prior to study entry must be present in his/her source documents. Additional testing to confirm these response categories will not be required and should be done at the discretion of the attending physician.

7.2.1.4.5 Evaluation of transfusion dependency

Transfusion dependency will be assessed at screening as well as during the course of the trial for all patients. Transfusion of blood products will be recorded in a separate module of the eCRF. The type and reason for transfusion, start and end date as well as the number of units will be captured at each visit with hematologic assessment.

A period of one week without any transfusion has been taken as a convention to define the status of transfusion independence to assess response. Any sample of peripheral blood which was taken within seven days after a transfusion will be considered as transfusion dependent.

For the definition of transfusion dependency, it does not matter which type of blood product was transfused. Moreover, the rules and time windows defined below apply not only to blood transfusions but also to erythropoietin, thrombopoietic agents and/or myeloid growth factors.

7.2.2 Safety and tolerability assessments

Safety will be monitored by assessing physical examination, vital signs, weight, performance status evaluation, ECG, cardiac imaging, ophthalmology examinations, laboratory evaluations as well as collecting all serious and non-serious Adverse Events (AE). For details on AE collection and reporting, please refer to [Section 8.1](#).

Clinically significant findings that were present prior to the signing of informed consent must be included in the Relevant Medical History/Current Medical Conditions page on the patient's eCRF. Significant new findings that begin or worsen after informed consent and meet the definition of an AE must be recorded on the Adverse Event page of the patient's eCRF.

7.2.2.1 Physical examination

A complete physical examination will be performed at screening at Day 1 of each cycle and at the EOT visit. Visit windows of \pm 4 days are allowed (except at cycle 1 Day 1). As specified in [Table 7-1](#), a screening physical examination performed prior to 4 days of first dosing does not need to be repeated at Cycle 1 Day 1.

The physical examination comprises a total body examination that should include: general appearance, skin, neck (including thyroid), eyes, ears, nose, throat, lungs, heart, abdomen, back, lymph nodes, extremities, vascular and neurological review. If indicated, rectal, external genitalia, breast and pelvis exams will be performed. Information about the physical examination must be present in the source documentation at the study site.

7.2.2.2 Vital signs

Vital signs (body temperature, pulse rate, blood pressure) will be monitored at screening, EOT, and before administration of BGJ398 at Day 1 of each cycle. Screening vital sign assessments performed within 4 days of first dosing do not need to be repeated at Cycle 1 Day 1. Vital signs will be measured according to normal medical practice.

7.2.2.3 Height and weight

Height and body weight will be measured. Weight will be measured at the screening visit, at Day 1 of each cycle, and at EOT. Screening weight assessment performed within 4 days of

first dosing does not need to be repeated at Cycle 1 Day 1. Height will be collected at screening only.

7.2.2.4 Ophthalmic examination

Ophthalmologic examination will be performed as indicated in [Table 7-1](#) which includes: visual acuity testing, slit lamp examination of the anterior eye segment, IOP, and fundoscopy. Additional examination methods such as specular microscopy (that enables a magnified, direct view of the corneal epithelium), corneal pachymetry, and dilated fundoscopy will be performed as clinically indicated.

7.2.2.5 Eastern Cooperative Oncology Group (ECOG) Performance status

Eastern Cooperative Oncology Group (ECOG) Performance status

The performance status will be assessed according to the ECOG performance status scale ([Oken 1982](#)). ECOG performance status will be assessed at screening, at Day 1 of each cycle and at the EOT visit ([Appendix N](#)). ECOG performance assessment performed within 4 days of first dosing does not need to be repeated at Cycle 1 Day 1.

7.2.2.6 Laboratory evaluations

Clinical laboratory analyses (hematology, biochemistry, coagulation, lipase, urinalysis, pregnancy test) are to be performed by the local laboratory according to the Visit Schedule outlined in [Table 7-1](#). Visit windows of \pm 4 days are allowed (except at cycle 1 Day 1). As specified in [Table 7-1](#), screening laboratory assessments performed prior to 4 days of first dosing do not need to be repeated at Cycle 1 Day 1. For patients with TIO diagnosis blood should be collected for FGF23 plasma assessment and 1-25-dihydroxy vitamin D. Novartis must be provided with a copy of the local laboratory's certification (if applicable), and a tabulation of the normal ranges and units of each parameter collected in the eCRF. Any changes regarding normal ranges and units for laboratory values assessed during the study must be reported via an updated tabulation indicating the date of revalidation. Additionally, if at any time a patient has laboratory parameters obtained from a different (outside) laboratory, Novartis must be provided with a copy of the certification and a tabulation of the normal ranges and units for this laboratory as well. The investigator is responsible for reviewing all laboratory reports for patients in the study and evaluating any abnormalities for clinical significance.

More frequent laboratory examinations may be performed at the investigator's discretion if clinically indicated.

At any time during the study, abnormal laboratory parameters which are clinically relevant and require an action to be taken with study treatment (e.g., require dose modification and/or interruption of study treatment, lead to clinical symptoms or signs, or require therapeutic intervention), whether specifically requested in the protocol or not, will be recorded on the Adverse Events eCRF page. Laboratory data will be summarized using the Common Terminology Criteria for Adverse events (CTCAE) version 4.0.3. Additional analyses are left to the discretion of the investigator.

7.2.2.6.1 Hematology

Hematology tests are to be performed by the local laboratory at screening, Days 1, 8, 15, 21 of Cycle 1 and Days 1 and 15 of Cycles 2, at Day 1 of each subsequent cycle and at EOT according to the Visit Schedule outlined in [Table 7-1](#). The hematology panel includes hemoglobin, hematocrit, platelet count, total red blood cells (RBC), total white blood cells (WBC) count, and a WBC differential including neutrophils, lymphocytes, monocytes, eosinophils and basophils.

7.2.2.6.2 Biochemistry

Biochemistry tests are to be performed by the local laboratory at screening, Days 1, 8, 15, 21 of Cycle 1 and Days 1 and 15 of Cycles 2, at Day 1 of each subsequent cycle and at EOT according to the Visit Schedule outlined in [Table 7-1](#). The full biochemistry panel includes blood urea nitrogen (BUN), creatinine, uric acid, sodium, magnesium, potassium, glucose, calcium, inorganic phosphate [Pi], LDH, total protein, albumin, bicarbonate, amylase, lipase, total cholesterol, high density lipoprotein (HDL), low density lipoprotein (LDL), and triglycerides. Additionally liver function test including AST/SGOT, ALT/SGPT, GGT, alkaline phosphatase, total, direct and indirect bilirubin will be measured.

7.2.2.6.3 Thyroid function

Thyroid function tests parameters include: thyroid stimulating hormone (TSH), free T3, and free T4.

Thyroid function should be assessed at screening, Day 1 of Cycle 1, Day 1 of Cycle 3, every 3 cycles from C3D1 during the treatment phase (or if clinically indicated), and at EOT.

7.2.2.6.4 Coagulation

International normalized ratio (INR) and pro-thrombin time (PT), activated partial thromboplastin time and fibrinogen will be measured at screening, Day 1 of Cycle 1, and during the treatment phase if clinically indicated.

7.2.2.6.5 Urinalysis

Urinalysis includes dipstick analysis of pH, bilirubin, ketones, leukocytes, protein, glucose, blood, and specific gravity, and will be performed at screening, Day 1 of each cycle and at EOT.

If clinically indicated based on macroscopic urinalysis results, a microscopic evaluation examination will be performed and will include Red Blood Cells, White Blood Cells, Casts, Crystals, Bacteria, and Epithelial cells.

7.2.2.6.6 Pregnancy and assessments of fertility

Women of childbearing potential must undergo a serum pregnancy test at screening to confirm eligibility in the trial (≤ 4 days before first dose of study drug), and at EOT. Women of child-bearing potential must additionally undergo a monthly urine pregnancy test during the treatment phase.

In case of pregnancy, the patient must permanently stop study treatment immediately, withdraw from the trial, and the pregnancy must be reported on the Clinical Trial Pregnancy Form.

7.2.2.6.7 FGF23 plasma and 1-25-dihydroxy vitamin D

For ongoing patients with TIO diagnosis FGF23 plasma levels and 1-25-dihydroxy vitamin D should be measured: at screening, C1D1 (if screening assessment occurred > 4 days from Cycle 1 Day 1), C1D15, and on Day1 of each subsequent cycles up to and including Day 1 of Cycle 4. Thereafter, should be measured every 16 weeks and EOT. A +/-4 days window is allowed for each assessment. Blood collection should be performed according to institutional guidelines.

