¹⁰ Phosphate binders should be given with meal (low phosphate diet), every day on days BGJ398 is given. No treatment with phosphate binders is needed during the BGJ398 off week in a cycle, unless the lab results indicate higher serum phosphorus levels that require continuous treatment with phosphate binders. Calcium-containing phosphate binders are not recommended.

¹¹ Only to confirm complete responses in patients with bone marrow tumor involvement prior to study treatment

¹² Information on the patient's chromosomal abnormalities/karyotyping based on documented history prior to study entry must be present in his/her source documents. Additional testing to confirm these response categories will not be required and should be done at the discretion of the attending physician.

¹³ For patients with a best response of Stable disease or better who discontinue study treatment due to disease progression, an optional tumor sample should be obtained for genomic analysis. For details, refer to [Section 7.2.4](#).

¹⁴ [REDACTED]

¹⁵ For patients with TIO diagnosis no prophylactic phosphate lowering therapy should be implemented

¹⁶ Only applicable for patient with TIO diagnosis. FGF23 plasma levels and 1-25-dihydroxy vitamin D should be measured: at screening, C1D1 (if screening assessment occurred > 4 days from Cycle 1 Day 1), C1D15, and on Day1 of each subsequent cycles up to and including Day 1 of Cycle 5. Thereafter, should be measured every 16 weeks and EOT. A +/-4 days window is allowed for each assessment

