7.1.2 Treatment period

Patients will be treated with BGJ398 (125 mg, orally, once-a-day,) until disease progression, unacceptable toxicity, death or discontinuation from the study treatment due to any other reason.

For details of safety and efficacy assessments, refer to [Table 7-1](#) and [Section 7.2](#).

- Visits and associated assessments that occur \pm 4 days from the scheduled date (except for cycle 1 Day1 where no visit window is allowed) will not constitute protocol deviations.
- The cycle length is 28 days. Day 1 of subsequent cycles will be calculated from cycle 1, day 1.
- Disease Assessments (per RECIST or appropriate hematological response criteria) must be performed every 8 weeks (\pm 4 days) after first dose of study drug (Day 1 of every odd cycle), until disease progression or end of treatment, whichever occurs first. Upon implementation of this amendment, the frequency of disease assessment will be reduced and evaluations should be every 16 weeks after the first 16 weeks on treatment.
- Laboratory assessments performed as part of the screening evaluations and within 4 days of the first dose of study treatment, are not required to be repeated on the first dosing day.
- [REDACTED]
- [REDACTED]
- For ongoing patients with TIO diagnosis FGF23 plasma assessment and 1-25-dihydroxy vitamin D will be collected, refer to [Table 7-1](#) and [Section 7.2.2.6.7](#).

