10.4 Primary objective

The primary endpoint is clinical benefit rate (CBR) in each group, with clinical benefit being assessed at 16 weeks.

For patients with solid tumors the assessment criteria will be RECIST 1.1 and will include responses of CR or PR or SD \geq 16 weeks. For hematologic tumors other appropriate hematological response criteria will apply and are included in the appendices.

For patients with TIO diagnosis without measurable/evaluable disease, the following criteria will be the assessment at 16 weeks:

- the tumor associated changes of metabolic parameters: plasma level of FGF23 < or =180 RU/mL; and inorganic phosphorous, calcium, and 1-25-dihydroxy vitamin D greater than the LLN (- 20%); and
- without requirement of supplementation therapy for at least the preceding cycle of the 16 week assessment.

For solid tumors, an assessment of CR or PR must be confirmed at least 4 weeks after initial observation, using RECIST 1.1. If the two assessments differ, the best response will be determined by [Table 3-3](#) of [Appendix A](#).

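### Section 7.2.2.6.7 and Table 7-1 differ by one cycle on FGF23 and vitamin D sampling, so the week-16 metabolic endpoint may be missed in some ongoing TIO patients

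*Protocol*

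**What the plan says.** Protocol Section 7.2.2.6.7, addressed to ongoing TIO patients, asks for FGF23 and 1-25-dihydroxy vitamin D at screening, at Cycle 1 Day 1 if screening was more than 4 days earlier, at Cycle 1 Day 15, and then on the first day of every later cycle "up to and including Day 1 of Cycle 4". It continues: "Thereafter, should be measured every 16 weeks and EOT". On timing it adds: "A +/-4 days window is allowed for each assessment".

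Note 16 of Table 7-1 (Section 7.1) gives the same time points, the same later interval and the same window, but its per-cycle sampling runs "on Day1 of each subsequent cycles up to and including Day 1 of Cycle 5".

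For TIO patients without measurable or evaluable disease, Section 10.4 states that "the following criteria will be the assessment at 16 weeks". It then requires FGF23, inorganic phosphorous, calcium and 1-25-dihydroxy vitamin D all to meet their limits, and no need for supplementation over at least the preceding cycle. Table 3-1 and SAP Section 6.1 place this assessment at the same time.

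Section 7.1.2 sends sites to both Table 7-1 and Section 7.2.2.6.7 for these two tests and does not say which governs.

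**The concern.** The one visit on which the two schedules differ is the visit at which the endpoint is assessed. If the Cycle 5 Day 1 sample is not drawn, two of the four laboratory components are absent at week 16. The components are all required, so clinical benefit cannot then be established. Section 10.4.4 rules out imputation of efficacy endpoints, and SAP Section 2 imputes nothing unless it says so. The evaluability rules in SAP Section 6.1 are written for CR, PR and SD and do not cover a missing metabolic result.

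The same measurements bear on Section 4.1.1, which ties continued treatment of TIO patients to metabolic benefit by week 16.

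There is also a compliance question. A site that omits the Cycle 5 Day 1 sample can be following Section 7.2.2.6.7 while departing from Table 7-1. As written, the protocol does not settle whether that is a deviation.

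**Working it through.** No power, alpha or sample-size figure is involved. The check is on visit dates.

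**Inputs.**
- Cycle length and anchor, Section 7.1.2: "The cycle length is 28 days. Day 1 of subsequent cycles will be calculated from cycle 1, day 1".
- 16 weeks = 112 days, as Appendix R itself equates them (Section 14.3.3.0).
- Visit window ±4 days, from both Section 7.2.2.6.7 and note 16.

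**Formula.** Days elapsed from Cycle 1 Day 1 to Day 1 of cycle n = (n − 1) × 28.
- Cycle 4 Day 1: 3 × 28 = 84 days, week 12.
- Cycle 5 Day 1: 4 × 28 = 112 days, week 16.

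**Schedules.** Each starts with Cycle 1 Day 15 (14 days, week 2). The later 16-week interval is counted in turn from the last per-cycle sample and from first dose.

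| Source | 16 weeks counted from | Sampling weeks | Sample within day 112 ± 4? |
|---|---|---|---|
| Section 7.2.2.6.7 | Cycle 4 Day 1 | 2, 4, 8, 12, 28, 44 | No |
| Section 7.2.2.6.7 | First dose | 2, 4, 8, 12, 16, 32, 48 | Yes |
| Table 7-1 note 16 | Cycle 5 Day 1 | 2, 4, 8, 12, 16, 32, 48 | Yes |
| Table 7-1 note 16 | First dose | 2, 4, 8, 12, 16, 32, 48 | Yes |

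**The failing case.** The next sample after Cycle 4 Day 1 is at 84 + 112 = 196 days, week 28. The nearest scheduled samples are 112 − 84 = 28 days before week 16 and 196 − 112 = 84 days after it. The windows do not close the gap. The latest permitted week-12 sample is day 88, the week-16 window is days 108 to 116, and the earliest permitted next sample is day 192. That leaves 108 − 88 = 20 days on one side and 192 − 116 = 76 days on the other.

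**What is still available at week 16.** Calcium and inorganic phosphate are in the biochemistry panel on Day 1 of every cycle (Section 7.2.2.6.2), so both are scheduled at Cycle 5 Day 1. A patient who fails on either, or who still needs supplementation, can be classed as not meeting the criteria without the other two tests. A patient who passes on these cannot be classed as a success.

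**Who is exposed.** The metabolic criteria apply only without measurable or evaluable disease. SAP Section 6.1 summarizes tumor response in TIO patients with a known underlying tumor type as for that type. As of Amendment 3 no new TIO patients are enrolled (Sections 5.1 and 5.2), so only patients already on study and short of week 16 can be affected.

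**The case against.** The strongest reply is that the sample is in fact scheduled. Section 7.1 presents Table 7-1 as the full list of assessments. Section 7.2.2.6, the parent laboratory section, directs clinical laboratory tests to that table. The table's grid marks both analytes on Day 1 of subsequent cycles, and note 16 names Cycle 5 Day 1. On this view a single digit in the text is outweighed. Most of this stands: a site working from the table collects the sample. It does not remove the inconsistency, because Section 7.1.2 cites the table and the section together and ranks neither.

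The second reply concerns the anchor. Elsewhere the protocol runs its 16-weekly disease assessments after the first 16 weeks of treatment and counts cycle days from Cycle 1 Day 1. Read that way, even the Cycle 4 wording yields a week-16 sample. This reading is possible, but Section 7.2.2.6.7 does not state it. Its sequence (per-cycle samples to Cycle 4, then the interval) is more naturally counted from Cycle 4 Day 1.

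Third, a patient whose end-of-treatment visit falls near week 16 is sampled then. That also stands.

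A reader might go further and infer that the week-16 endpoint goes unmeasured in all ongoing TIO patients. The documents do not support that. The gap needs both the section and the Cycle 4 anchor to be followed, and TIO patients with measurable disease are not judged on the metabolic criteria alone.

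A reader might also infer damage to the trial's primary Bayesian analysis. That is not shown either. TIO is not among the six groups in Section 10 and has no control rate in Table 14-1 or in SAP Table 1. An added cohort enters the model only with minimum enrollment and a reasonable control-rate estimate, and the documents do not say whether TIO would qualify.

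**Conclusion.** This is an internal inconsistency in operative text. The two places differ by one cycle, and the cycle in question carries the week-16 primary assessment for TIO patients without measurable or evaluable disease. Under one of the two readings of Section 7.2.2.6.7, no FGF23 or 1-25-dihydroxy vitamin D sample falls within 20 days of the week-16 window. Under the other reading, and under Table 7-1, the sample is taken.

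The size is small. Loss of the endpoint requires an ongoing TIO patient without measurable or evaluable disease who has not reached week 16, at a site that follows the section and counts from Cycle 4 Day 1, with no end-of-treatment visit near week 16. The documents give no count of such patients. SAP Section 2 reports that most subjects had already stopped study treatment, so the number may be very small or zero. For any patient it does reach, clinical benefit could not be established and would not be imputed. This is a minor correction, worth making because the intended week-16 assessment is clear and the repair is nearly free.

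**What to change.** Reconcile Section 7.2.2.6.7 with note 16 of Table 7-1 and with the 16-week endpoint in Section 10.4. Both places should schedule FGF23 and 1-25-dihydroxy vitamin D at Cycle 5 Day 1. Both should also state where the later 16-week interval is counted from, so that the schedule can be read only one way.

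The cost is one digit and one short clause of text. Table 7-1 already contains the sample, so no visit or test is added to the schedule there, and no sample-size, alpha or power figure changes.
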